Tryon, W. (2005). The reliability and validity of two ambulatory monitoring actigraphs. *Behavior research methods*, 37, 492-497

APPENDICES

Modified Pittsburgh Sleep Index

Sydney Local Health District

MODIFIED PITTSBURGH SLEEP QUALITY INDEX (PSQI)

ID NUMBER: _____

Instructions: The following questions relate to your usual sleep habits during the Past week only.

During the past week,

1. When have you usually gone to bed? _____
2. How long (in minutes) has it taken you to fall asleep each night? _____
3. When have you usually gotten up in the morning? _____
4. How many hours of actual sleep do you get at night? _____

5. During the past week, how often have you had trouble sleeping because you...	Not during the past week (0)	Less than once a week (1)	Once or twice a week (2)	Three or more times a week (3)
a. Cannot get to sleep within 30 minutes				
b. Wake up in the middle of the night or early morning				
c. Have to get up to use the bathroom				
d. Cannot breathe comfortably				
e. Cough or snore loudly				
f. Feel too cold				
g. Feel too hot				
h. Have bad dreams				
i. Have pain				
j. Other reason(s), please describe, including how often you have had trouble sleeping because of this reason(s):				
6. During the past week , how often have you taken medicine (or asked a nurse for tablet) to help you sleep?				
7. During the past week, how often have you had trouble staying awake while eating meals, or engaging in social activity?				
8. During the past week, how much of a problem has it been for you to keep up enthusiasm to get things done?				
	Very good (0)	Fairly good (1)	Fairly bad (2)	Very bad (3)
9. During the past week, how would you rate your sleep quality overall?				

[figure not shown]
Sleep Diary

[figure not shown]
	LAST NIGHT I WENT TO BED AT	LAST NIGHT I FELL ASLEEP AT	OVERNIGHT MY SLEEP WAS DISTURBED BY	THIS MORNING I WOKE UP AT	THIS MORNING I GOT OUT OF BED AT	MY SLEEP QUALITY WAS	DID YOU HAVE A NAP DURING THE DAY	HOW LONG
DAY 1						 Very Good  Good  Average  Bad  Very Bad	 Yes  Nohours minutes
DAY 2						 Very Good  Good  Average  Bad  Very Bad	 Yes  Nohours minutes
DAY 3						 Very Good  Good  Average  Bad  Very Bad	 Yes  Nohours minutes
DAY 4						 Very Good  Good  Average  Bad  Very Bad	 Yes  Nohours minutes
DAY 5						 Very Good  Good  Average  Bad  Very Bad	 Yes  Nohours minutes

Visual Analogue Scale : Sleep Quality

How was your sleep?

0
Barely
slept

2
Very poor

4
Poor

6
Average

8
Good

[figure not shown]

10
Excellent

Ward Poster : A Good Night's Sleep

A GOOD NIGHT'S SLEEP

DURING THE DAY

ENJOY THE SUN!

EXERCISE!

GET UP! DON'T STAY IN
BED

KEEP UP THE ROUTINES

[figure not shown]
EAT RIGHT

Coffee is okay ☺

[figure not shown]
CHILL AND LISTEN TO
MUSIC!

NO NAPPING!

A GOOD NIGHT'S SLEEP

LATE AFTERNOONS & EVENINGS

NO NAPPING!

AVOID COFFEE!

AVOID LATE-NIGHT TV

[figure not shown]
AVOID COKE

AVOID BIG MEALS

AVOID SMOKES &
ALCOHOL

CHILL AND LISTEN TO
MUSIC!

ONLY STAY IN BED IF
YOU'RE READY TO
SLEEP!

Patient Autonomy and Satisfaction Survey

PATIENT AUTONOMY AND SATISFACTION SURVEY

(Modified Healthcare Climate Questionnaire – HCCQ)

Participant ID:

Please answer the questions below regarding your relationship with your health care practitioners for the Sleep Program.

Practitioners have different styles in dealing with patients. Your responses will be kept confidential, so none of the practitioners will know your responses. Please be honest and candid.

Choose your answers using the scale below for each question by filling in the blank after each question with a number from 1 to 7.

	2	3	4	5	6	7
Strongly disagree	Moderately disagree	Slightly disagree	Neutral	Slightly agree	Moderately agree	Strongly agree

1. I feel that my health care practitioner has provided me choices and options about treating my sleep.	_____
2. I feel my health care practitioner understands how I see things with respect to my health.	_____
3. I am able to be open with my health care practitioner about my health.	_____
4. My health care practitioner conveys confidence in my ability to make changes regarding my health.	_____
5. I feel that my health care practitioner accepts me whether I follow their recommendations or not.	_____
6. My health care practitioner has made sure I really understand things that I do which might impact on my sleep, and the benefits of changing these behaviours without pressuring me to do so.	_____
7. My health care practitioner encourages me to ask questions.	_____
8. I feel a lot of trust in my health care practitioner.	_____
9. My health care practitioner answers my questions related to my sleep fully and carefully.	_____
10. My health care practitioner listens to how I would like to do things regarding my sleep.	_____
11. My health care practitioner handles my emotions very well.	_____
12. I feel that my health care practitioner cares about me as a person.	_____
13. I don't feel very good about the way my health care practitioner talks to me about my health.	_____
14. My health care practitioner tries to understand how I see my sleep habits before suggesting any changes.	_____
15. I feel able to share my feelings with my health care practitioner	_____

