In conclusion, scientific research suggests that in the clinical setting, actigraphy is reliable for evaluating sleep patterns in patients with insomnia, for studying the effect of treatments designed to improve sleep, in the diagnosis of circadian rhythm disorders (including shift work), and in evaluating sleep in individuals who are less likely to tolerate PSG, such as inpatient psychiatric patients. While actigraphy has been used in research studies for many years, it is only recently that the methodological issues have been systematically addressed in clinical research and practice. With those issues addressed, the use of actigraphy is now being applied to clinical practice. (Ancoli-Israel et al, 2003).

STUDY OBJECTIVES

Primary Objective

To evaluate the effect of the Sleep Program on duration of admission in HDU (compared to controls) and sleep duration (Actigraphy data), in male psychiatric HDU inpatient participants.

Secondary objectives

1. Sleep quality - improvement in the Pittsburgh Sleep Quality Index
2. Sleep efficiency- percentage time in bed vs percentage time asleep
3. To test the engagement (tolerability and practicality) with a structured Stimulus Control Therapy Program
4. Impact on use of as needed (PRN) hypnotics
5. To describe the characteristic of sleep, activity and light exposure of patients in a high dependency psychiatric unit using wrist actigraphy.

Hypotheses

- We hypothesise that a structured stimulus control program for sleep will shorten duration of admission at psychiatric HDU.
- There will be an improvement in the sleep duration and efficiency
- There will be an improvement in the quality of sleep via a reduction of the self-rated Pittsburgh Sleep Quality Index score, measured at the beginning and end of the study.
- Participants in the Bright Light Study will engage in a structured stimulus control therapy program and it will be well-tolerated.

STUDY DESIGN

Design, Study Groups, Number of Participants

This is a pilot study for a complex intervention and we do not know the effect of variance. We seek to test our methodology, exterminate recruitment and retention rates, feasibility and finally, determine the sample size. We also seek to highlight any issues with acceptability, compliance, and delivery of our interventions.

Number of centres

Single-centre, at [name] Centre, male High Dependency (psychiatric) Unit

Duration

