These sessions are held as a mini picnic with healthy snacks. During these sessions, printouts will be discussed individually with participants, especially with respect to their self-evaluation in their Sleep Diaries. This aims to increase insight and empower the participants to take a proactive role in their management.

As a group, the registrars will give further psychoeducation about sleep, with a focus on sleep hygiene, and addressing specific stimuli which affect sleep.

Wednesday sessions are also repeated in a weekly cycle. Patients in their initial and final weeks of the program will be asked to complete the Pittsburgh Sleep Quality Index, modified to reflect the quality of sleep within one week.

Session 3

Session three are held on Fridays and are repeated on a weekly basis. It is split into two components. Firstly, the morning session is in the form of a breakfast barbeque – which is open to the entire ward to participate. Facilitators of sessions 1 and 2 are able to join. This session is an informal way for participants and clinicians to freely exchange ideas and feedback, as well as to reinforce sleep psychoeducation provided in earlier sessions.

Secondly, there will be a booster session on Friday evenings, which is self-directed by the participants and is optional. It entails participants making use of the ward measures made available to them – to enhance relaxation and stimulus control.

Summary table of sessions

Session	Day and time	Content	Measurement tools	
			Sleep diary	Actigraphy
1	Monday 11:30am – 12pm	
 • Cooking group • Preliminary psychoeducation • Program information and obtaining consent • Providing actigraph watch and diary for participant 	X	X
	Tuesday	Nil active intervention for Day 2 participants complete diary +/- nurse Day8 participants - maintain stimulus control and am light goggles	X	X
2	Wednesday (Pre- session)	
 • Collecting watches + analysing actigraphy 	X	X
	Wednesday 11:30am – 12pm	
 • Outdoor session with snacks • Psychoeducation about • Stimulus Control Therapy, Sleep Hygiene • Present sleep results • Administer PSQI and one-item Sleep Quality measure (start and terminating session only) 		
	Thursday		X	X
3	Friday AM	
 • Outdoors session with bacon and eggs 	X	X

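### The one-week PSQI keeps a response option that no non-zero weekly count can fit, so its frequency items move in uneven steps and a zero can be scored two ways

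*Protocol*

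**What the plan says.** The protocol's description of Session 2 has participants complete the PSQI in their first and last weeks, "modified to reflect the quality of sleep within one week". The form in the appendices agrees: "The following questions relate to your usual sleep habits during the Past week only".

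The frequency columns on that form are "Not during the past week (0", "Less than once a week (1", "Once or twice a week (2" and "Three or more times a week (3". The number that ends each label is its score. As the form reads here, these columns head items 5a-5j, 6, 7 and 8. Item 9, on overall sleep quality, has its own columns from very good to very bad. Item 8 asks "how much of a problem has it been for you to keep up enthusiasm to get things done".

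Improvement in the PSQI is the first secondary objective, and the administrative table lists it among the key secondary outcomes. The Hypotheses section expects better sleep quality "via a reduction of the self-rated Pittsburgh Sleep Quality Index score". The Statistical Analysis Plan section says effects will be estimated as within-person mean differences. The protocol gives no rule for combining the items of the modified form into a total.

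**The concern.** The recall window is one week, but the column scored 1 is worded as a rate below one per week. That wording makes sense only over a longer window. Over one week an event either did not happen or happened at least once, so the column duplicates zero and leaves nothing to separate one bad night from two.

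At stake is the reading of the start-to-end PSQI change. If an item's score does not rise evenly with the number of bad nights, the same improvement earns different points depending on where a patient starts. If a patient with no episodes has two correct boxes, the score can change when sleep has not. Using the same form twice does not cancel either fault. An analysis plan cannot fully repair them later either, because the form never records whether a patient had one bad night or two.

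**Working it through.** **Inputs, all from the form in the appendices.** Recall window: 7 nights. Scores: 0, 1, 2, 3 with the labels quoted above. The protocol states no figure to reproduce here.

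**Step 1: items affected.** Items 5a-5j are 10 items; adding 6 and 7 gives 12. Item 8, as read, is a 13th. With item 9 there are 13 + 1 = 14 rated items. Items 1-4 are open answers and are unaffected.

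**Step 2: match each possible count to the labels.**

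| Episodes in the week | Labels that fit | Score |
|---|---|---|
| 0 | none; fewer than one | 0 or 1 |
| 1 | one or two | 2 |
| 2 | one or two | 2 |
| 3 to 7 | three or more | 3 |

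Score 1 is reached only by a patient whose true count is zero. Counting episodes rather than nights changes nothing, since any whole number from 3 up still scores 3.

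**Step 3: step sizes.**
- One episode to none: 2 - 0 = 2 points.
- Two episodes to one: 2 - 2 = 0 points.
- None at both visits: 0 points if the same box is ticked, 1 point up or down if not.

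On a scale of none, one, two, three or more (0, 1, 2, 3), these become 1, 1 and 0.

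**Step 4: does this push the change in one direction?** This is an illustration on assumed values. Let the number of bad nights K be Binomial(7, p), and let every zero be scored 0. Expected item scores are:
- form as worded: 2·P(K = 1 or 2) + 3·P(K ≥ 3)
- even scale: P(K = 1) + 2·P(K = 2) + 3·P(K ≥ 3)

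The two differ only by P(K = 1), where P(K = 1) = 7p(1 - p)^6. So the drop on the form minus the drop on the even scale equals P(K = 1) at the start minus P(K = 1) at the end. For p from 0.10 to 0.05 that is 0.372 - 0.257 = 0.115, which matches the first row below (0.462 - 0.347).

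| Nightly p, start to end | Drop, form | Drop, even scale | Ratio |
|---|---|---|---|
| 0.10 to 0.05 | 0.462 | 0.347 | 1.33 |
| 0.20 to 0.10 | 0.660 | 0.665 | 0.99 |
| 0.30 to 0.15 | 0.756 | 0.905 | 0.84 |
| 0.50 to 0.25 | 0.781 | 1.038 | 0.75 |
| 0.70 to 0.50 | 0.213 | 0.264 | 0.81 |
| 0.80 to 0.40 | 0.471 | 0.601 | 0.78 |

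The form can overstate, understate or barely alter an item's change, depending on baseline frequency. The table leaves out the noise from the ambiguous zero.

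**The case against.** The best defence is that this is one badly worded label on a secondary questionnaire in an open-label pilot. The section on sample size ties planning to actigraphic sleep duration, not to the PSQI. Sleep quality is also captured by the visual analogue scale, the diary ratings and PSQI item 9, none of which has this fault. Patients may also read the label loosely, as hardly ever, and use it as a mild category. All of this limits the consequence. None of it repairs the form: loose reading by some patients and literal reading by others is itself a source of noise.

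Several stronger readings are tempting, and the protocol does not support them.

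- **That the PSQI result is biased in a known direction.** Items 1-4 lie outside the scale, no combining rule is given, and the illustrative ratios fall on both sides of 1. Uneven steps and added noise are shown; a direction is not.
- **That 13 of 14 items are certainly affected by the recall change.** Item 8 asks about severity, so its mismatch with frequency columns is a separate fault. A header of its own may also have been lost when the PDF was read. The firm count is 12.
- **That the flat top of the scale belongs to the same defect.** Everything from three nights up scores 3, but that stays true under the fix proposed below, so it should not be charged to this label.
- **That the five-row sleep diary leaves part of each week unrecorded.** Nothing says that one sheet serves a week. The protocol describes a continuing record, and further sheets can be issued.

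**Conclusion.** The point stands in a limited form. As worded, the frequency columns do not suit a one-week recall: score 1 fits no non-zero count, zero fits two boxes, and one and two episodes are merged. This applies to 12 of 14 rated items, or 13 if item 8 is printed under the same columns. Per item, the first bad night is worth 2 points, the second is worth none, and an unchanged zero can shift by 1.

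The conclusion rests on literal reading of the labels and on whole-number counts within the week. It needs no assumption about sample size, variance or effect size. The ratios of 0.75 to 1.33 rest on assumed nightly probabilities and show only that the direction is open. The size of the effect on the PSQI total cannot be derived from the protocol. The PSQI change and its variance, as pilot estimates, are what suffer; the actigraphic primary outcome is not affected.

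**What to change.** Before first enrolment, replace the response options for items 5, 6 and 7 with the number of nights in the past week (days for item 7): none (0), one (1), two (2), three or more (3). This keeps the 0-3 range, makes every level attainable and gives zero a single box. Check the printed form for item 8: if it stands under the frequency columns, give it its own severity options from no problem to a big problem, to match its question.

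The cost is a reprint of one paper form. The administrative table says recruitment has not begun, so no data would have to be converted. Once forms have been completed, a recode could merge scores 0 and 1, but it could not tell one bad night from two.

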	Ward environmental initiatives
Stimulus Control Therapy	
 • Consistent wake time at 7am encouraged by ward staff • Beanbags: an alternate place to sit other than the bed
Sleep Psycho-education	
 • Visual cues regarding specific sleep hygiene strategies around patient room and ward area. • Reinforcement, encouragement and further psychoeducation provided by nursing staff
Increased light exposure (regulating circadian rhythm)	
 • Using available open spaces wherever possible enhanced with early morning Retimer™ blue-green light goggles for those with sleep-phase delay
Relaxation	
 • Calming music during wind down • Quiet space with dim lights and beanbags

Activity Groups

Each participant will be invited to participate in thrice-per-week, 30-minute workshops in the program, which aim to provide psychoeducation about sleep, debriefing and sleep-promotion related

activities. It is also aimed at increasing daytime activity and enforcing a regular circadian rhythm. This is conducted on a repeated weekly cycle as outlined below. These sessions will take place on the outdoor area of the HDU (the balcony) where possible such that participants will receive continuous daylight exposure during these sessions. Each session will take place in mid-morning to lunchtime.

Session 1

Session 1 are on Mondays. They are facilitated by a senior Occupational Therapist and a peer-support worker and is designed to instil a routine of activity (via a Cooking group). Initial consenting and program information will be provided to a patient who is commencing. As well, actigraph watch and sleep diary will be provided to the commencing participant, allowing for ongoing record and feedback of their sleep parameters throughout their time in the program. Qualitative feedback regarding sleep will be collected during these sessions.

Session 2

Second sessions are held on Wednesdays, on the balcony of the HDU. They are facilitated by two psychiatry registrars. Prior to the sessions, participants' actigraph watches are collected and sleep data analysed by the research assistant. A visual representation of sleep duration and activity for each patient will be printed prior to the session and given to the registrars, and printouts are identifiable only by participant IDs.

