- familial distress
- harm to any member of a vulnerable population
- reputational harm

Informed Consent Process

There is a one-stage consent process to entry into the study. The Senior occupational therapist, [name] (investigator in this study) will introduce the study and discuss the main aspects to potential eligible participants in person in the first instance to reduce medical-patient power imbalance.

Participants will receive the study information sheets in hard copy. Research clinicians will discuss the study with participants in light of the information provided to them. The research clinician will obtain written content from patients willing to participate.

A potential participant has one week to consider their participation; however, they may defer that decision up until two weeks prior to their expected discharge date from the HDU - given a meaningful study period is defined as a minimum of two weeks of participation.

Enrolment Procedure

The participant will be enrolled into the study after the informed consent process has been completed and the participant has met all inclusion criteria and none of the exclusion criteria.

Participants need to be inpatient at HDU North (male) in PMBC, Royal Prince Alfred Hospital.

Participants are first identified as potential (candidate) participant by medical/OT/SW/RN from Multi-Disciplinary Team (MDT) meeting, satisfying inclusion and exclusion criteria.

The participant will receive a study enrolment number (Participant ID number), and this will be documented in secure and confidential register, as well as in the medical records.

Capacity

Potential (candidate) participants are clinically assessed for the ability to understand and capacity to give consent. The consultant in the treating team must deem the candidate participant as having capacity to consent; and this must be a consensus impression by the rest of the MDT. Further, it must be verifiable by demonstrated understanding and engagement with the Sleep Program. Mental state is monitored on an ongoing basis as per standard care. In cases where a participant deteriorates or loses capacity to consent and participate altogether: their involvement in the study will cease. This is outlined under *Early Terminations*.

Randomisation Procedure

Not applicable

Adverse Event Reporting

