- 2) A factor found on examination of the device (a deterioration in characteristics or performance)

De-identified Serious Adverse Event Reports will be completed as required throughout the study period and sent the ethic committee.

Early Termination

Possible circumstances for early termination of the study include:

1. Early termination initiated by patient due to side-effects, change-of-mind, intolerability, or the perception that their sleep have improved sufficiently such that they no longer require participation in the program.
2. Loss of capacity to consent due to deterioration or variation in mental state
3. Loss of ability to participate due to deterioration or variation in mental state
4. Medical admission of patient due to an acute medical illness whilst inpatient at PMBC
5. Transfer of patient to a different facility.

The study coordinator will be responsible for correspondence with HREC.

Investigators involved in implementing the Sleep Program clinically, can receive formal notification of termination from the participant by verbal or written form. They may receive notice of termination through a delegate (such as the participant's nurse or medical officer responsible). The investigator will need to formally inform the Study Coordinator in written form.

The Study Coordinator will then be required to document termination in digital study data for this participant – whose data will be separated from overall data pool. Early termination data will be kept for discussion purposes but will be excluded in results and statistical analyses.

The Study Coordinator will be responsible for informing the

(who is responsible for what aspect in the process of terminating the study (informing participants, correspondence to HREC, compiling a final study report, unbinding if applicable)).

BLINDING AND UNBLINDING

- a) Blinding (Masking): This trial is an open-label with no attempt at masking
- b) Emergency unblinding: not applicable

STATISTICAL CONSIDERATIONS

Sample Size or Power Calculation

The pilot study will determine the sample size. Power calculation will be the minimum number of samples required to provide adequate power for the primary outcome. (Actigraphic changes in sleep duration)

Statistical Analysis Plan

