Given the pilot study nature we will describe the sample, and the outcomes using but only use analytical techniques to estimate potential effects using difference of means within person measures in SPSS. The pilot study is unlikely to generate sufficient data points for bivariate or multivariate regression modelling.

DATA SECURITY, STORAGE AND ARCHIVING OF STUDY DOCUMENTS

Data Safety and Storage

There are two forms of data collected in pilot study: digital data, and physical data handwritten on paper forms.

Digital Data

Patient name, MRN and date of birth are linked to a Participant ID number. This is kept on an Excel spreadsheet, which is password protected on a single desktop issued by the Sydney Local Health District. The computer will be kept on-site only, in the secured, staff-only section of PMBC, which is accessible via swipe card only. The patient data spreadsheet can only be accessible within a Sydney LHD premises which has access to the SLHD intranet. Back-up copy of this spreadsheet is kept within the Sydney LHD ICT infrastructure.

De-identified digital data includes all data that are entered digitally, and are only identifiable through Participant ID. This includes any digitised data from physical forms, actigraphy data, aggregate length-of-stay data, and so on. Computers with access to these files that are password-protected and individualised for the investigator.

For security, a complete back-up of the data will be kept on a separate, secure Sydney LHD laptop, and is performed on a daily basis. Periodic data analysis files will also be backed-up and kept. Primary access to the Sydney LHD computing facilities will be through physical access onsite and through the intranet. Security will be enforced through restricted, swipe-card physical access, passwords and different levels will be assigned to groups and individuals.

Physical Data

Physical data includes the following; patient-completed self-assessment forms (PSQI, sleep diary, Visual scales), equipment check-in and check-out equipment logs. These are identifiable to patient with *only* the Participant ID.

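### The satisfaction survey assures participants that no practitioner will know their answers, but the identifier on the form and the data access described do not secure that assurance

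*Protocol*

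**What the plan says.** The survey in the protocol's appendices is a 15-item rating form adapted from a healthcare climate questionnaire. It states whom it rates: "Please answer the questions below regarding your relationship with your health care practitioners for the Sleep Program". It then gives an unqualified assurance, "Your responses will be kept confidential, so none of the practitioners will know your responses", and asks for candour. The head of the form has a field for the "Participant ID".

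Elsewhere the protocol describes how that identifier and the study data move:

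- Enrolment Procedure: when the identifier is issued, "this will be documented in secure and confidential register, as well as in the medical records".
- Session 2: the sleep printouts are "given to the registrars, and printouts are identifiable only by participant IDs", and in the session "printouts will be discussed individually with participants".
- Early Termination: the text refers to "Investigators involved in implementing the Sleep Program clinically", so some investigators are also Program staff.
- Digital Data: de-identified data, including what is digitised from paper forms, are indexed by the identifier and held on computers that are "password-protected and individualised for the investigator". The same section says that different access levels will be assigned.
- Physical Data: original study forms are entered on the computer, and the paper is kept in a secure cabinet in the staff-only part of the centre.

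The Administrative Information table lists autonomy and participant satisfaction among the key secondary outcomes.

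**The concern.** The people rated by the survey appear to be among those who can both recognise the identifier and open the data filed under it. The protocol's safeguards (identifier in place of name, passwords, swipe-card area, locked cabinet) guard against outsiders. None is stated to separate the rated staff from the ratings.

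Two things are at stake. The first is measurement. Men in a high dependency unit are asked to rate staff involved in their care, on items about trust, handling of emotions and how they are spoken to. If a respondent doubts that the form is private, the easy answer is the favourable one. One aim of the pilot is to bring out problems of acceptability, so candid criticism is what it needs most. The second is participant protection: a written assurance to psychiatric inpatients should be one that the data handling supports.

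**Working it through.** There is no figure to reproduce. The check is whether the protocol's own text links a completed form to a rated practitioner, one step at a time.

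1. **Is the form anonymous?** No. It carries the "Participant ID".
2. **Can Program staff resolve the identifier?** Yes, by two routes. It is entered in the medical records (Enrolment Procedure), which treating staff use. And the registrars who run Session 2 hold printouts that bear only the identifier, yet must discuss each with the right man (Session 2), so they have to know whose it is. With about 4 to 6 participants in the program at any time (Duration), matching is easy.
3. **Are any of the rated staff investigators?** Yes. Early Termination says so in general terms. A specific case also follows from two sections: the Activity Groups text has a senior Occupational Therapist facilitating Session 1, and the Informed Consent Process describes the senior occupational therapist as an investigator in the study.
4. **Do survey answers enter data that investigators can open?** On the general wording, yes. Physical Data has original study forms entered on the computer, and Digital Data puts digitised forms in the identifier-indexed files on investigators' computers. The survey is not named in the list of physical data, so this step rests on the general wording.
5. **Is there a stated barrier between the rated staff and individual answers?** No. Access levels are announced in Digital Data, but nothing says what they permit or whom they exclude. No independent collector and no sealed return are described.

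Steps 1 to 3 are explicit or follow directly from the text. Step 4 is a fair reading of general wording. Step 5 is an absence, and it matters because the form makes a definite promise that depends on such a barrier.

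The protocol recognises the hazard in another place: under Informed Consent Process it chooses who first introduces the study so as to lessen the imbalance of power between doctor and patient. The survey has no comparable provision.

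**The case against.** The strongest objection is that being able to resolve an identifier is not the same as seeing the answers. Confidential does not mean anonymous, and a coded form can be kept confidential if the right person handles it. This stands. A reader might infer that the promise is broken, or that practitioners will read the surveys; the protocol does not support that. No section says that a registrar, occupational therapist, peer worker or nurse collects, enters or reads this form.

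Second, the access wording is thin. It speaks of the investigator in the singular, and the same section provides for different access levels, which could be set to keep facilitators out. This also stands, and it is why the conclusion is that the assurance is unsecured, not that it is breached. It does not dispose of the point, because the protocol never says that the levels will be used in this way.

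Third, who collects a form is often settled in operating procedures, and the consent pages are not in the copy reviewed. That would answer a complaint about missing detail. Here the participant-facing form makes an unqualified promise, and following the written form and data flow leaves that promise unsupported.

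Fourth, response bias is an inference. The form tells respondents that their answers are private, and many may believe it. That is fair: the protocol makes bias plausible but does not show it. A reader might want to put a number on it. The protocol gives no basis for one: it states no scoring rule or total score, and item 13 is worded negatively, so even the effect of a given shift on a raw sum would depend on how that item is handled.

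**Conclusion.** The point holds in this form: the assurance that no practitioner will know the responses is not secured by the access the protocol describes, and the autonomy and satisfaction ratings are open to favourable response bias of unknown size.

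It rests on two readings: that the survey is among the study forms digitised under the identifier, and that investigators who deliver the Program have the access to study files that the protocol gives to investigators. If the access levels were already set to exclude these staff from individual answers, the remaining fault would be that the protocol does not say so.

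The reach is limited. Two of several key secondary outcomes in an open-label, descriptive pilot are affected. Actigraphic sleep duration is not, nor is the sample-size planning based on it. The change is still worth making before recruitment, because it is cheap and because the assurance is given directly to participants.

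**What to change.** 1. Replace the "Participant ID" on this form with a separate survey code. The key is held by someone who neither treats participants nor runs sessions; the research assistant who analyses the actigraphy would serve, if independent in that sense.
2. Have the form returned sealed to that person, who also enters it.
3. State in Digital Data that the access levels bar session facilitators and treating staff from individual survey answers, and that they receive aggregate results only. Apply the same rule to the paper forms.
4. If this cannot be done, reword the assurance so that it describes who will in fact be able to see the answers.

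Removing every identifier from the form may look simpler, but it would conflict with Early Termination, which requires the data of participants who stop early to be separated and left out of the results. A form with no code could not be traced for that purpose, whereas a separate code with a protected key allows it.

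The cost is a code key to maintain, envelopes, and one access restriction. No planned analysis is lost: the Statistical Analysis Plan section proposes description and within-person mean differences, and links satisfaction to no other measure.
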